### 5.2 Notification of safety and protective measures (HRO Art. 20)

The project leader is promptly notified (within 24 hours) if immediate safety and protective measures have to be taken during the conduct of the research project. The Ethics Committee will be notified via BASEC of these measures and of the circumstances necessitating them within 7 days.

### 5.3 Serious events (HRO Art. 21)

A serious event is defined as any adverse event where it cannot be excluded, that the event is attributable to the collection of health-related personal data using the WD, and which:

- requires inpatient treatment not envisaged in the treatment protocol or extends a current hospital stay;
- results in permanent or significant incapacity or disability; or
- is life-threatening or results in death.

If a serious event occurs, the research project will be interrupted and the Ethics Committee notified on the circumstances via BASEC within 7 days according to HRO Art. 21 [1]. The project leader will submit a report to the responsible Ethics Committee which evaluates the relationship between the event reported and the methods of collecting health related personal data within the project, and propose how to proceed with the project.

During this study the included patients are undergoing clinical procedures as per standard of care for their cancer diagnosis, which will cause side events unrelated to the study procedures and will not be reported.

#### **5.4 Procedure for investigations involving radiation sources**

No radioactive sources are used in this research project.

#### **5.5 Amendments**

Substantial changes to the project set-up, the protocol and relevant project documents will be submitted to the Ethics Committee for approval according to HRO Art. 18 before implementation. Exceptions are measures that have to be taken immediately in order to protect the participants.

#### **5.6 End of project**

Upon project termination, the Ethics Committee is notified within 90 days. All health-related data are anonymized upon termination of data analysis. Records and documents pertaining the conduct of this study, including source documents, CRFs and consent forms will be retained for 10 years.

#### **5.7 Insurance**

In the event of project-related damage or injuries, the liability of the Inselspital Bern provides compensation, except for claims that arise from misconduct or gross negligence.

### **6 FURTHER ASPECTS**

#### **6.1 Overall ethical considerations**

The research project will be carried out in accordance to the protocol and the Declaration of Helsinki, the guidelines of Good Clinical Practice (GCP) and the ISO Norm 14155, the Swiss Law and Swiss regulatory authority's requirements. The CEC will receive annual safety reports and will be informed about study stop/end in agreement with local requirements.

The study can only begin once approval from all required authorities has been received. Any additional requirements imposed by the authorities shall be implemented.

#### **6.2 Risk-Benefit Assessment**

For the participants this study has minimal risks:

- Pressure: If the WD is attached too tight, this can result in pressure and stasis injuries.
- Skin reactions: Allergic reactions to the materials used, skin reactions because of moisture or dirt between the skin and the device, or skin reactions to friction of the device against the skin may occur.
- Child distress: Young children may not understand the purpose of this study and of wearing the WD. Therefore, they could show symptoms of distress as persisting crying and resistance against attachment of the WD.

Training and information of parents and of patients if applicable, will minimize these risks. The WD is fitted using body size-appropriate elastic bands. After fitting, the size of the band cannot

by tightened any further by the patient. Regular cleaning of the skin underneath the device and of the device itself will be instructed.

In this study, there are no direct benefits for the patients. The knowledge gained from this study, and potential future studies building upon the results of this study may help to provide better care for future pediatric patients, including pediatric patients undergoing chemotherapy for cancer.

### **6.3 Rationale for the inclusion of vulnerable participants**

Health data in children and adolescents is known to differ in many core characteristics from health data in adults and can therefore not be extrapolated from adults. To assess feasibility of continuous monitoring of health data in pediatric patients specifically, children and adolescent need to be studied themselves, despite them being especially vulnerable study participants.

## **7 QUALITY CONTROL AND DATA PROTECTION**

### **7.1 Quality measures**

For quality assurance the Ethics Committee may visit the research sites. Direct access to the source data and all project related files and documents must be granted on such occasions. All staff involved are trained in project related procedures and all important aspects.

### **7.2 Data recording and source data**

Baseline patient data and information on disease and treatment, where relevant, will be extracted from electronic medical records. Investigators and staff of the study site delegated to complete CRFs will record study-related information on patients.

Data recorded by the WD will be transferred to the mobile phone via Bluetooth and then uploaded in a pseudonymized fashion to a web-based password-protected dashboard. The WD cannot be linked with other devices and recorded data cannot be read by third parties, nor by the parents and patients. Biovotion is ISO 13485 certified [24] and guarantees data security in compliance with the EU General Data Protection Regulation. Biovotion will provide an application programming interface, so that the investigators can download the data themselves. Access and retrieval of the data from the dashboard is secured by a password. All data are transferred and stored using encryption (TLS, https).

Source documents include the patients' charts (electronic as well as paper), which are stored at the site-specific usual location for charts. Data recorded by the WD will be downloaded by the investigators and stored electronically in a SharePoint Databased provided by the CTU Bern. This database will be used as source document for the WD data, as the web-based dashboard is not convenient for long term data storage.

If parents and patients if applicable consent, collected data will be published in anonymized form. Study-specific documents (Informed Consent Forms, screening form, patient identification list and relevant correspondence) are filed in the Investigator Site File. The Investigator Site File is stored in a closed location of the "study center".

### **7.3 Confidentiality and coding**

Project data will be handled with uttermost discretion and is only accessible to authorized staff who require the data to fulfill their duties within the scope of the research project. On the CRFs and other project specific documents, participants are only identified by a unique patient number (ID). The patient identification list will be stored by the project leader.

Confidentiality of the patients will be maintained by assigning a unique patient number (ID), keeping identifiers separate from the data and storing data in a locked file with password access and secure computer database in line with Swiss legal requirements. Scientific reports generated from the study will not contain information that would identify the participating children. Biovotion Zurich signed a data processing agreement and agrees not to try to re-identify the pseudonymized data and to maintain confidentiality about all information.

### **7.4 Retention and destruction of study data and biological material**

Source documents and documents pertaining to the conduct of this study, including CRFs, and consent forms, are archived for a minimum of 10 years after the completion or premature termination of the study.

## **8 FUNDING / PUBLICATION / DECLARATION OF INTEREST**

Funding for this study will be searched by grant applications to the “Batzebär” foundation and, for backup, to the “Berner Stiftung für Krebskranke Kinder und Jugendliche”. These institutions will have no influence on the study design, data collection and analysis, decision to publish, or preparation of the manuscript.

The main results of this study will be communicated to the parents and the patients if applicable, and the treating staff involved in a letter written in lay language.

The detailed study results will be submitted for publication in peer-reviewed journals. The current version of the ICMMJE recommendations regarding authorship eligibility is applicable.

The use of professional writers is not planned.

The protocol is not confidential; it is intended to be made publicly available.

There is no conflict of interest for the Sponsor-Investigator and for all study investigators.

## Appendix 1: Fitzpatrick Scale

The Fitzpatrick skin type classification denotes six different skin types [22, 25]. The scale is based on a questionnaire related to an individual's genetic constitution, reaction to sun exposure and tanning habits. The response to all questions are added to get the final score (all tables from: Sachdeva S. Fitzpatrick skin typing: Applications in dermatology. Indian J Dermatol Venereol Leprol 2009 [25])

Table A1: Genetic disposition, total score 0-16

Score	0	1	2	3	4
What is the Colour of your eyes?	Light blue, grey, or green	Blue, grey, or green	Blue	Dark brown	Brownish black
What is the natural colour of your eyes?	Sandy red	Blond	Chestnut/dark blond	Dark brown	Black
What is the colour of your skin in the nonexposed areas?	Reddish	Very pale	Pale with beige tint	Light brown	Dark brown
Do you have freckles in the nonexposed areas?	Many	Several	Few	Incidental	None

Table A2: Reaction to sun exposure, total score 0-16

Score	0	1	2	3	4
What happens when you stay in sun too long?	Painful redness, blistering, peeling	Blistering followed by peeling	Burns sometimes followed by peeling	Rare burns	Never had burns
To what degree do you turn brown?	Hardly or not at all	Light color tan	Reasonable tan	Tan very easy	Turn dark brown quickly
Do you turn brown within several hours after sun exposure?	Never	Seldom	Sometimes	Often	Always
How does your face react to the sun?	Very sensitive	Sensitive	Normal	Very resistant	Never had a problem

Table A3: Tanning habits, total score 0-8

Score	0	1	2	3	4
When did you last expose the body to sun (or artificial sunlamp/tanning cream)?	More than 3 months ago	2-3 months ago	1-2 months ago	Less than a month ago	Less than 2 weeks ago
Did you expose the area to be treated to the sun?	Never	Hardly ever	Sometimes	Often	Always

Table A4: Total score of table A1 to A3 corresponding to Fitzpatrick skin Type

Skin type score	Fitzpatrick skin type
0-7	I
8-16	II
17-25	III
25-30	IV
over 30	V-VI

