### A. Secondary feasibility-related outcomes:

A1) At least acceptable quality scores (Q.2 to Q.4 and Q.6/7) of further signals (S.2 to S.4 and S.6/7 (see 2.3) during a cumulative duration of ≥18/24h per day (midnight to midnight), during ≥7 consecutive days within the 14 days of study duration (binary outcomes, measured once).

A2) Cumulative length of time with at least acceptable quality scores Q.1 to Q.4 and Q.6/7 (see 2.3) per study day (continuous outcomes, measured daily).

A4) Primary outcome and secondary outcomes A1 and A2 by skin type according to the Fitzpatrick scale [22] (Appendix 1).

A4) Primary outcome and secondary outcomes A1 and A2 by activity reported by parents and patients if applicable.

A5) Proportion of patients and parents indicating that continuous monitoring with the WD is acceptable per day and per entire study duration (binary outcome, measured daily plus once).

A6) Reasons not to wear the device as reported by parents and by patients if applicable (categorical outcome, measured daily).

A7) Side effects reported by parents and patients, if applicable (categorical outcome, measured daily)

A8) Effort (cumulative number and duration of contacts) per study day for the investigators (continuous outcomes, measured daily).

B) Secondary comparison-related outcomes:

B1) Difference between discrete measurements performed for clinical routine cares of heart rate and the mean of continuously measured signal S.1 (heart rate) within +/-10min at times of the discrete measurement (continuous outcomes, measured potentially multiple times).

B2) Like B1, for percutaneously measured blood oxygenation and signal S.2 (Oxygen Saturation).

B3) Like B1, for respiration rate and signal S.3 (respiration rate).

B4) Like B1, for ear temperature and signal S.4 (core temperature).

B5) Like B1, for ear temperature and signal S.5 (skin temperature).

C) Secondary outcomes for the exploration of specific patterns

C1) Exploration of potential changes in or specific patterns of the measured signals S.1 to S.9 and quality scores Q.1 to Q.6, within 48 hours before and after clinical diagnosis of fever (ear temperature of  $\geq 39.0^{\circ}\text{C}$ , or  $\geq 38.5^{\circ}\text{C}$  if fever is declared for clinical reasons) with or without neutropenia and microbiologically or clinically defined infections, if applicable.

C2) Like C1) for further signals collected with the WD.

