## 3 PROJECT POPULATION AND STUDY PROCEDURES

### 3.1 Project population, inclusion and exclusion criteria

Inclusion criteria:

- Chemotherapy treatment because of any malignancy, expected to last  $\geq 1$  month at time of recruitment for myelosuppressive therapy; or at least one cycle of myeloablative therapy requiring autologous hematopoietic stem cell transplantation.
- Age from 1 month to 17.99 years at time of recruitment
- Written informed consent from patients and/or parents

Exclusion criteria:

- Local skin diseases prohibiting wearing of the WD.
- Denied written informed consent from patients and/or parents

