#### 3.1.1 Study visit

The study visit will be done during a routine outpatient visit, or during hospitalization. One of the study investigators will distribute the WD, the charger, and if needed the mobile phone to the parents or patient. Parents and/or patients, with no suitable mobile phone, will be provided with a phone for the study time. This phone will not be usable for other purposes than data transfer. Basic characteristics as age, height, weight, thigh and arm circumference and skin type will be assessed at the study visit.

The WD is fitted using body size-appropriate elastic bands and the fitting is controlled by the investigator. Parents and patients if applicable, will be instructed in the handling and charging of the WD. For instructions, the pictures and descriptions provided by the manufacturer on the website, in the “instructions for use” handbook and the information in the study information form will be used. Instruction on how to install the mobile phone app for data transfer will be provided (see 7.2). The WD will be put on the upper arm or, if anatomically reasonable, on the upper leg.

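### The Appendix 1 skin-type score has a double-assigned cut-off, a misworded item and no rule for children without sun history

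*Combined protocol and SAP*

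**What the plan says.** Section 2.4 (Primary and secondary endpoints) lists, as the first of two items numbered A4: "Primary outcome and secondary outcomes A1 and A2 by skin type according to the Fitzpatrick scale". Section 3.1.1 says when the variable is obtained: "thigh and arm circumference and skin type will be assessed at the study visit". The eligible ages in section 3.1 are "Age from 1 month to 17.99 years at time of recruitment".

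Appendix 1 is the only place that turns answers into a type. It has ten items, each scored 0 to 4, in three tables: A1 ("Genetic disposition, total score 0-16"), A2 ("Reaction to sun exposure, total score 0-16") and A3 (tanning habits, 0-8). The rule is "The response to all questions are added to get the final score". Table A4 maps the sum to types: 0-7 is I, 8-16 is II, 17-25 is III, 25-30 is IV, and over 30 is V-VI. The appendix attributes all its tables to a cited dermatology article.

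The plan does not say who answers for a young child or how an item that does not apply is scored. Section 4.2 says only that missing data are not imputed.

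(Two sets of labels collide here. Below, outcome A4 means the endpoint in section 2.4; Table A1 to Table A4 mean the tables of Appendix 1.)

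**The concern.** Appendix 1 is the working instrument for a listed secondary outcome, so a fault in it goes straight into how patients are grouped. Three features stand out.

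1. The bands for types III and IV share the value 25, and no tie rule is given. Two assessors could class the same child differently, and both would be following the plan.
2. Table A1 first asks for eye colour and then asks "What is the natural colour of your eyes", with answers running from sandy red through blond to black.
3. The sun-reaction and tanning items presuppose a history that a young infant may not have. The type such a child receives then depends on a convention that the plan does not state, and not only on skin colour.

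At stake is whether outcome A4 describes signal quality by skin type in a consistent and reproducible way across the whole age range.

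**Working it through.** **Inputs (all from Appendix 1).** Table A1 has 4 items, Table A2 has 4 and Table A3 has 2, each scored 0-4. The bands are those of Table A4.

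**Reproducing the printed ranges.** Table A1: 4 × 4 = 16. Table A2: 4 × 4 = 16. Table A3: 2 × 4 = 8. The total runs from 0 to 16 + 16 + 8 = 40, which is 41 possible totals. The printed sub-score ranges are correct.

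**Mapping every total from 0 to 40 to a type.** Every total has at least one type. Exactly one total, 25, has two (III and IV). One in 41 counts possible values and does not estimate the share of patients affected; the documents give no score distribution.

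**The second item of Table A1.** It can move the total by at most 4 points. That is a ceiling: the answers offered make the intended question fairly plain.

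**Share of points that need a sun history.** Table A2 + Table A3 = 16 + 8 = 24 of 40.

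**A never-exposed infant, answered literally.** Table A2: never burned = 4, hardly or no tanning = 0, never browns within hours = 0, face never a problem = 4, so 4 + 0 + 0 + 4 = 8. Table A3: the second item's never option = 0. The first item has no never option, and the longest interval, the nearest answer, also scores 0. The total is therefore (Table A1) + 8. With Table A1 from 0 to 16, it runs from 8 to 24: type II (8-16) or type III (17-24). Removing the overlap in either direction leaves this unchanged, because 25 is not reached.

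**Other ways of handling the same infant, with Table A3 = 0:**

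| Handling | Table A2 | Total | Types reachable |
|---|---|---|---|
| Literal answers | 8 | 8-24 | II, III |
| Never burned, face reaction normal | 4+0+0+2 = 6 | 6-22 | I, II, III |
| Never burned, face item scored 0 | 4+0+0+0 = 4 | 4-20 | I, II, III |
| All sun items blank, counted as 0 | 0 | 0-16 | I, II |
| Sun items missing, not imputed | none | none | no type |

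In none of these rows does the darkest colouring (Table A1 = 16) score above 24. With Table A3 = 0, type IV needs at least 9 points from Table A2 (16 + 9 = 25, itself the ambiguous value). Type V-VI starts at 31 and so needs at least 31 − 16 = 15 points from the sun and tanning items.

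**The case against.** The strongest objection is that a reader might infer more than the form shows.

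- **That an infant can only be type II or III.** The documents do not support this. With Table A3 = 0 it holds only when Table A2 sums to exactly 8, and the plan does not prescribe those answers. The table above shows I-III, I-II or no score under other handling. What stands is that the plan has no rule, and that in each case examined the upper types are out of reach.
- **That the 4 or more patients under 6 years are all affected.** Section 2.5 sets a minimum for under-6s, not for infants. Nothing shows that a child of 2 to 5 years lacks a sun history. The number of never-exposed infants is not given and could be zero.
- **That a real effect of skin colour on signal quality would be hidden.** Section 4.1 plans descriptive statistics and no hypothesis is stated for outcome A4. Twenty patients spread over five bands could hardly establish or exclude such an effect under any scoring. Even under literal answers, the lightest and darkest infants get different types (II and III).
- **That the misworded item misclassifies patients.** No route to a wrong answer is shown. Eye colour has just been asked and the options point to hair, so this is a wording correction.
- **That winter timing distorts Table A3.** Section 4.3 plans the first recruitment in December and the last patient out in March. If recent sun is rare in those months, most patients would score low together, which is mainly a common shift.

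It is also fair to say that the overlap and the wording may come from the cited article, which was not available for checking. That bears on how to correct them, not on whether the form is workable as printed. Finally, replacing the named scale by a single item would be a matter of preference and would lose the published score; adding a breakdown does not have that cost.

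**Conclusion.** The point stands in limited form and should be fixed, because the cost is close to nothing. The double assignment of 25 and the repeated eye question are visible on the page and need no assumption, except that hair is meant, which is inferred from the answer options. The absence of a rule for children without sun history is also plain. Its consequence, a total confined to 8-24, rests on literal answers and on taking Table A3 as 0.

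The size is small. One of 41 totals has no unique type, the misworded item carries at most 4 points, and the infant problem touches an unstated and possibly very small number of patients in a descriptive secondary outcome. The primary outcome and the claim of feasibility at 15 of 20 do not use skin type. The documents do not support calling the score systematically wrong, or saying that outcome A4 would miss a true effect because of it.

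**What to change.** 1. Check the cited source, then make bands III and IV mutually exclusive. Bands of 17-25 and 26-30 would follow the table's own pattern, in which each earlier band starts one above the end of the one before; 17-24 and 25-30 would also remove the overlap.
2. Correct the second item of Table A1 to hair colour if the source confirms it.
3. Keep the full score as the grouping for outcome A4 in patients who can answer the sun-exposure items, and state that no total-score type is assigned to children without sun history.
4. For all patients, add a breakdown of outcome A4 by the Table A1 item on skin colour in unexposed areas. It is already on the form and can be observed at any age. Merge sparse levels.

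The cost is a correction to a short form, one extra descriptive table, and fewer patients in the full-score breakdown. No new data item is needed.
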